5.3.10 Concomitant Medication

Concomitant medication and concomitant therapy will be summarised as number of subjects being treated with each type of medication/therapy classified according to Anatomical Therapeutic Chemical (ATC) level 3 and WHO Drug Dictionary preferred term. The safety set will be used for these presentations.

The medications will be divided between those ongoing before baseline (start and end date before baseline) or as ongoing after baseline (starting before or after baseline, and stop date, or still ongoing, after baseline). Listing of concomitant medication will include all medications including an indicator of above defined time intervals.

If the start date of a concomitant medication is missing, it will be assumed that the medication started before treatment. If the date is partially missing, the year and month, if available, will be used to decide whether the medication started before baseline or after baseline. In summary tables, each subject is only counted once for each drug.

The safety set will be used for these presentations.

5.3.11 Adverse Events

AEs will be coded according to the Medical Dictionary for Regulatory Activities (MedDRA) system and tabulated by System Organ Class (SOC) and by Preferred Term (PT).

A summary table will be presented with No. of subjects with AEs, No. of subjects with serious AEs, No. of subjects with severe AEs, No. of subjects with ADRs (probable or possible), Number of subjects with at least one AE leading to discontinuation, and also the number of AEs, severe AEs, serious AEs, ADRs (where a certain AE is only counted once within each subject on a preferred term level).

The total number of subjects with at least one AE and the number of AEs will be derived and summarised by SOC and PT.

Similar tables will be created for serious adverse events.

AEs will also be tabulated by severity (mild, moderate and severe) and relationship to treatment (probable, possible, unlikely or not applicable). Adverse events occurring or worsening after first treatment will be included in summary tables. Any AEs reported before first treatment will only be included in listings.

In listings of AEs the relative day counted from first administration of IMP (Day 1) will be presented together with the relative day from the latest administration of IMP (the actual dates will also be included).

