The most common AE was cough, reported for 21/30 (70%) subjects receiving molgramostim nebuliser solution and 8/12 (67%) receiving placebo. The AEs considered treatment-related reported by two or more (>5%) subjects receiving molgramostim nebuliser solution were: cough (50%), productive cough (10%) and headache (6.7%). Cough was considered treatment-related for a similar proportion of subjects receiving placebo (58%). Number of cough events were 48 in 30 subjects in the combined molgramostim groups and 15 in 12 subjects in the placebo groups. A higher number of treatment-related AEs were observed in the 600 µg dose level compared to the 300 µg dose level and placebo in the MAD part. There were no serious adverse events (SAEs), severe AEs, dose-limiting toxicity, or other remarkable findings of clinical concern from review of clinical safety data. Further details are available in the Investigator's Brochure (IB).

Previous experience of inhaled rhGM-CSF in PAP patients

Based on the findings that PAP may be caused by autoantibodies to GM-CSF, off-label administration of subcutaneous and inhaled rhGM-CSF in the marketed formulations (molgramostim and sargramostim) has already been explored in the clinic. The results have indicated that therapy with rhGM-CSF can offer an effective and safe treatment for the patient with aPAP. In a recent meta-analysis, including three subcutaneous studies and two inhalation studies, a 59% pooled response rate was calculated with a higher response observed with inhalation use [2].

The majority of aPAP patients participating in published clinical studies using inhaled rhGM-CSF have been treated with sargramostim (approximately 70 patients). Improved pulmonary function was reported from all studies. In three of the six studies the alveolar-arterial oxygen difference ((A-a)DO₂) has been assessed as a measure of response to

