11.3 Reporting of Adverse Events

All trial subjects will be carefully monitored for the occurrence of AEs during the trial period from Screening (Visit 1) to the completion of the 48-week Follow-up visit (Visit 13). The investigator will collect AEs with a non-leading question such as "have you experienced any new health problems or worsening of existing conditions" as well as reporting events directly observed or spontaneously volunteered by subjects.

Clearly related signs, symptoms and abnormal diagnostic procedure results should be grouped together and reported as a single diagnosis or syndrome whenever possible.

All AEs including but not limited to events reported by the subject, or reported in answer to an open question by the investigator or member of this team, which fall into any of the above definitions must be recorded as an AE in the eCRF and should include the following information:

- Brief description of the event (diagnosis)
- Start date (and time, if relevant)
- Stop date (and time, if relevant) (or resolution)
- Severity
- Action taken regarding trial drug
- Opinion on causality
- Seriousness

Outcome

Severity

Severity describes the intensity of an event, and will be assessed as:

Mild

The AE is easily tolerated and does not interfere with daily activity.

Moderate

The AE interferes with daily activity, but the subject is still able to function. Medical intervention may be considered.

Severe

The AE is incapacitating and requires medical intervention.

If an AE changes in severity, it should be reported as an AE of new severity but with the same description.

Causality

Causality will be assessed as:

Probable

A clinical event, including laboratory test abnormality, with a reasonable time sequence to administration of the IMP, unlikely to be attributed to concurrent disease or other drugs or chemicals, and which follows a clinically reasonable response on withdrawal (dechallenge). Rechallenge information is not required to fulfil this definition.

Possible

A clinical event, including laboratory test abnormality, with a reasonable time sequence to administration of the IMP, but which could also be explained by concurrent disease or other drugs or chemicals. Information on IMP withdrawal may be lacking or unclear.

Unlikely

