12.1.12 Adverse Events

Adverse events will be coded using the Medical Dictionary for Regulatory Activities (MedDRA) and tabulated by system organ class (SOC) and by preferred term (PT).

The total number of subjects with at least one AE and the total number of AEs will be presented.

The number of subjects and the number of AEs will be tabulated by SOC and by PT.

AEs will also be tabulated versus worst severity and worst relationship to treatment.

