2.2 Secondary Efficacy Endpoints

Key Secondary Endpoints:

- Change from baseline in 6-minute walking distance (6MWD) after 24-weeks treatment
- Change from baseline in SGRQ total score after 24-weeks treatment
- Time to WLL during 24-weeks treatment
- Number of AEs, SAEs, ADRs, severe AEs and AEs leading to treatment discontinuation, including clinically significant changes in laboratory tests and

echocardiographic (ECG) variables, during 24-weeks treatment (hereafter described under Safety Endpoints)

Further Secondary Endpoints:

- Number of WLL over time during 24-weeks treatment (Added in SAP).
- Absolute change from baseline in VC (% predicted), DLCO (% predicted), FEV₁ (% predicted), FVC (% predicted) and relative change from baseline in PaO₂ after 24-weeks treatment
- Number of subjects with >5 mmHg/>0.67 kPa and number of subjects with >10 mmHg/>1.33 kPa improvement in (A-a)DO₂ after 24-weeks treatment
- Number of subjects with >5 percentage points and number of subjects with >10 percentage points improvement in VC (% predicted) after 24-weeks treatment
- Number of subjects with >10 percentage points improvement in DLCO (% predicted) after 24 weeks treatment
- Number of subjects with >10 percentage points improvement in FEV₁(% predicted) after 24-weeks treatment
- Number of subjects with >10 percentage points improvement in FVC (% predicted) after 24-weeks treatment
- Number of subjects with >10% relative improvement in PaO₂ after 24-weeks treatment
- Number of subjects with improved tolerance to exercise (increase in distance walked ≥50 m or desaturation <4 percentage points on the 6MWT) after 24-weeks treatment
- Change from baseline in dyspnoea score and cough scores after 24-weeks treatment
- Number of subjects with improved CT score after 24-weeks treatment

Exploratory Endpoints

Double-blind treatment period

- Absolute change from baseline of (A-a)DO₂, VC (% predicted), DLCO (% predicted), FEV₁(% predicted), FVC (% predicted), and relative change from baseline in PaO₂ after 4 and 12-weeks treatment
- Time period during which the (A-a)DO₂ level is maintained below Baseline minus 10mmHg
- Number of subjects with improved tolerance to exercise (increase in distance walked ≥50 m or desaturation <4 percentage points on the 6MWT) after 4 and 12-weeks treatment
- Time period during which the improvement in tolerance to exercise is maintained
- Change from baseline in dyspnoea score and cough scores after 4 and 12-weeks treatment

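### The overall AE summary table reports subject-by-preferred-term pairs where the key secondary safety endpoint and Protocol 12.1.12 call for numbers of events

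*SAP*

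**What the plan says.** Protocol 10.2.2.1 and SAP 2.2 define the key secondary safety endpoint as a count: "Number of AEs, SAEs, ADRs, severe AEs and AEs leading to treatment discontinuation", over 24 weeks of treatment. Protocol 12.1.12 matches this. Overall, "The total number of subjects with at least one AE and the total number of AEs will be presented", and at the next level "The number of subjects and the number of AEs will be tabulated by SOC and by PT". It gives no collapsing rule.

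SAP 5.3.11 describes one overall summary table holding numbers of subjects and numbers of AEs, severe AEs, serious AEs and ADRs. A parenthesis on the event counts adds "where a certain AE is only counted once within each subject on a preferred term level". For discontinuations the table gives only the "Number of subjects with at least one AE leading to discontinuation". The next SAP paragraph, without the parenthesis, says "The total number of subjects with at least one AE and the number of AEs will be derived and summarised by SOC and PT", with similar tables for serious AEs.

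SAP 5.1 lists four changes from the protocol. The AE counting rule is not one of them. On data capture, Protocol 11.3 says: "If an AE changes in severity, it should be reported as an AE of new severity but with the same description".

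**The concern.** A count that admits each preferred term once per subject is not a number of events. It says how many different terms each subject had, summed over subjects. Two arms with the same subjects affected by the same terms get the same figure, however often the events recur in each arm. The table would still label that figure as a number of AEs, and a reader would take it as the endpoint.

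This matters because Protocol 5.3 names pulmonary effects, including cough and dyspnoea, as the potential dose-limiting toxicity, and such symptoms can recur. One arm also alternates weekly between active and placebo for 12 cycles. An event that resolved and returned in each active week would count the same as a single occurrence. The stake is descriptive safety reporting on a named endpoint.

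**Working it through.** **1. What each planned output counts** (SAP 5.3.11 and SAP Appendix 1, double-blind period)

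| Category | Endpoint asks for | Overall summary table | Other planned tables |
|---|---|---|---|
| AEs | events | subject-PT pairs | 14.3.1.2 by SOC/PT: number of AEs, no restriction stated |
| SAEs | events | subject-PT pairs | 14.3.1.5 by SOC/PT: no restriction stated |
| Severe AEs | events | subject-PT pairs | 14.3.1.3: subjects only |
| ADRs | events | subject-PT pairs | 14.3.1.3: subjects only |
| AEs leading to discontinuation | events | subjects | none (listing 14.3.2.3) |

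At preferred-term level a collapsed count equals the subject count. The SOC/PT sentence asks for both, which makes sense only if every event is counted there. The SAP does not say so. On that reading, Tables 14.3.1.1 and 14.3.1.2 carry the same label for different quantities and will not reconcile. A repeated severe AE or ADR would enter the all-AE count in 14.3.1.2, but no table would show the repeat as severe or related.

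**2. Illustration with the phase I cough data** (Protocol 5.1)

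Inputs: cough in 21 of 30 molgramostim and 8 of 12 placebo subjects; for events, "Number of cough events were 48 in 30 subjects in the combined molgramostim groups and 15 in 12 subjects in the placebo groups".

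- Protocol percentages reproduced: 21/30 = 70% and 8/12 = 67%.
- All events per subject: 48/30 = 1.60 and 15/12 = 1.25; ratio 1.60/1.25 = 1.28.
- Each subject once: 0.70 and 0.67; ratio 1.05.
- Events dropped: (48 − 21)/48 = 27/48 = 56% and (15 − 8)/15 = 7/15 = 47%.

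**3. Exposure and precision of that illustration**

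Protocol 5.1 gives 12 active and 6 placebo subjects in the single-dose part, 18 active and 6 placebo subjects dosed daily for six days, and all 42 completing.

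- Doses, taking all as given: active 12 × 1 + 18 × 6 = 120; placebo 6 × 1 + 6 × 6 = 42.
- Events per dose: 48/120 = 0.40 and 15/42 = 0.36; ratio 1.12.
- Crude Poisson standard error of the log ratio: √(1/48 + 1/15) = 0.296. The 95% intervals are about 0.72 to 2.29 for 1.28, and 0.63 to 2.00 for 1.12.

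More than half of the apparent 28% excess comes from the larger share of active subjects in the multiple-dose part. What remains is compatible with no difference.

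**4. When collapsing matters** (assumption, not from the documents)

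Take one preferred term that recurs as a Poisson process, with mean λ events per placebo subject and a true rate ratio of 2. The expected share of subjects counted is 1 − exp(−λ) on placebo and 1 − exp(−2λ) on active.

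| λ | 0.25 | 0.5 | 1 | 2 | 3 |
|---|---|---|---|---|---|
| Ratio after collapsing | 1.78 | 1.61 | 1.37 | 1.14 | 1.05 |

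The loss is small for rare events and nearly complete for frequent ones. The summary table pools all terms, so its attenuation would depend on the mix.

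**The case against.** The other side has four sound arguments.

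- **Scope.** A reader might infer that the SAP discards every recurrence. The documents do not support that. The parenthesis belongs to the summary-table sentence, the SOC/PT sentence carries no restriction, and listings 16.2.7.1 and 16.2.7.2 hold individual events. Nor does the pooled count merely repeat the subject count: a subject with three different terms adds 1 to subjects and 3 to collapsed AEs. The two coincide only at preferred-term level.
- **The cough figures.** Cough is a single term and has no row in the summary table, so those figures describe no output that the rule is stated to govern. They pool 150, 300 and 600 µg in healthy volunteers, and the protocol itself calls the incidence similar. Reading them as a hidden difference between arms is not justified.
- **Purpose.** Because a severity change creates a new record, a plain count of records would count one episode more than once. The rule does prevent that.
- **Inference.** SAP 5.4 restricts the confirmatory procedure to the primary and three key secondary efficacy parameters. AE counts are not tested.

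All four stand, and they narrow the point. None explains why a table meant to deliver a number of events should deliver something else under that label, or why severe AEs and ADRs have no event count in any table. Preventing double counting of one episode does not require dropping separate episodes.

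**Conclusion.** The point holds for the overall summary table. Followed as written, that table does not report the stated endpoint for AEs, SAEs, severe AEs or ADRs, and it departs from Protocol 12.1.12 without being declared in SAP 5.1. The gap is widest for severe AEs and ADRs, whose same-term recurrences remain visible as such only in listings, and for AEs leading to discontinuation, which have no event count. For all AEs and SAEs the gap is smaller. It rests on reading the SOC/PT sentence as a count of all events, which is natural but unstated.

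The size in this trial cannot be computed from the documents, because it depends on how often terms recur within subjects. The phase I figures and the Poisson range show only the direction and the conditions under which it matters. It would be wrong to infer that a safety signal is being concealed, or that alpha, power or any confirmatory conclusion is at risk.

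**What to change.** In SAP 5.3.11, make the overall summary table show, for AEs, SAEs, severe AEs, ADRs and AEs leading to discontinuation, both the number of subjects and the total number of events. Define an event as one continuous episode: consecutive records with the same term that differ only in severity are merged and counted once at worst severity, while separate episodes each count. If subject-by-term pairs are kept as well, label them as such. State the same event rule for the SOC/PT tables so that totals reconcile with the summary. List any remaining departure from Protocol 12.1.12 in SAP 5.1.

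The cost is SAP wording and a small programming rule. The AE fields in Protocol 11.3 include start and stop dates but no identifier linking severity-change records, so the link has to be made from term and dates. Ambiguous cases can be settled in the blind data review before unblinding. No new data collection is needed.

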5.3.12 Other Safety Assessments

Any safety assessments described in this section will be summarised in a similar manner for the double-blind and follow-up period, if applicable.

Vital Signs

For vital signs parameters (systolic and diastolic blood pressure, heart rate, respiratory rate and oral body temperature) summary statistics will be produced for observed values by visit.

In addition, the difference from baseline to each visit at which they were assessed will be derived and presented.

Shift tables that show the number of subjects that changed from normal, abnormal (not clinically significant) or abnormal (clinically significant) at baseline to the state at each post-baseline time of assessment will be presented.

Clinical Laboratory Measurements

Clinical laboratory measurements will be assessed at screening, baseline and each visit during the double-blind treatment and follow-up period.

Haematology includes: Haemoglobin, Red Blood Cell Count (RBC), Red Blood Cell Distribution Width (RDW), Haematocrit (PCV/EVF), Mean cell volume (MCV), Mean cell haemoglobin (MCH), Mean cell haemoglobin concentration (MCHC), Platelet count, White cell count, and white cell differential absolute count and percentage: Neutrophils, Lymphocytes, Monocytes, Eosinophils, Basophils, and Prothrombin Time International Normalised Ratio (PT-INR).

Clinical Chemistry includes: Aspartate Aminotransferase (AST), Alanine Aminotransferase (ALT), Gamma Glutamyl Transpeptidase (GGT), Alkaline Phosphatase, Bilirubin, Urea, Creatinine, Potassium, Sodium, Calcium, Chloride, Phosphate, Total protein, Albumin, LDH, C-Reactive Protein (CRP), and Glucose (non-fasting).

Specifically for France, Urinalysis includes: Dipstick measuring for proteinuria, haematuria, glucosuria and nitrite; and microalbuminuria test.

For all laboratory parameters, summary statistics will be produced for observed values by visit. In addition, the difference from baseline to each visit at which they were assessed will be derived and presented. The number of normal, abnormal and clinically significant observations will be tabulated for each treatment group by visit, and in corresponding shift tables from baseline to each following visit. Abnormal values will be flagged in listings.

For laboratory values which are below the limit of quantification, the value corresponding to the limit of quantification will be used when summarising data (e.g. if the result is <0.5 then the value 0.5 will be used in the statistical analysis).

ECG

Electrocardiogram parameters (heart rate, QRS, PR and QT intervals) will be summarised, together with changes from Baseline. Corrected QT will be calculated using Fridericia's formula (QTcF) and summarised, together with changes from Baseline.

Overall interpretation of ECG, normal, abnormal not clinically significant or clinically significant abnormalities will be tabulated by visit and data will be presented in shift tables, where data before baseline is cross-tabulated versus data at later assessments.

Physical Examination

Any abnormal findings in physical examination are reported as medical history or adverse events. Overall interpretation of whether any abnormalities were observed (Yes/No) will be presented in shift tables where data before baseline is cross-tabulated versus data at later assessments.

CT Scan

Occurrence of adverse findings at week 24 compared to Baseline (Yes/No) will be summarised. Description of any adverse findings will be listed.

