Based on information from similar products, the potential dose-limiting toxicity of molgramostim would be based on pulmonary effects, such as bronchoconstriction, dyspnoea, cough or decreased pulmonary function. Pulmonary function and respiratory symptoms will be monitored during the trial and double-blind trial treatment should be discontinued if significant worsening occurs. If there is significant systemic exposure, haematologic findings such as leucocytosis and neutrophilia may occur. Therefore, laboratory safety monitoring will be conducted during the Double-blind treatment period. As non-clinical data on similar products indicate that systemic exposure to rhGM-CSF may be associated with increased pre- and post-implantation losses, pregnancy testing will be performed in women of childbearing potential prior to dosing, at monthly intervals during the Double-blind treatment period and the open-label treatment Follow-up period.

Treatment with molgramostim nebuliser solution is expected to be more effective, less invasive, and more convenient, than the currently available symptomatic treatment, WLL, for patients with aPAP. In the current trial two thirds of the subjects will receive active drug and one third will receive placebo. Rescue treatment with WLL will be available for all subjects who experience any unacceptable lack of response or disease progression during the trial. Subjects requiring WLL during the Double-blind treatment period will continue trial treatment.

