12.1.13 Other Safety Assessments

Physical Examination

Physical examination data will be summarised, together with changes from Baseline.

Vital Signs

Vital signs will be summarised, together with changes from Baseline.

ECG

Electrocardiogram parameters (heart rate, QRS, PR and QT intervals) will be summarised, together with changes from Baseline. QTcF will be calculated and be summarised, together with changes from Baseline.

Laboratory Safety Assessments

For laboratory data, summary statistics will be produced for observed values and for changes from Baseline to each visit. Abnormal values will be flagged in listings.

Shift tables will show the number of subjects who changed from below, within or above the reference range at baseline to below, within or above the reference range at end of treatment.

For laboratory values which are below the limit of quantification, the value corresponding to the limit of quantification will be used when summarising data (e.g. if the result is <0.5 then the value 0.5 will be used in the statistical analysis).

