5.1 Changes in the Planned Analyses

This SAP is based on protocol versions and amendments described in section 1. Compared to these, the following changes have been implemented in the SAP:

- All model-based analyses will include adjustment for a dichotomous categorization of country as Japan vs other countries.
- A number of additional subgroup analyses were added, as described in section 5.8.
- An additional sensitivity analysis for the primary endpoint was added for handling of subjects who had a WLL (section 5.3.6)
- Number of WLLs over time, was included as a further secondary endpoint in the double-blind period, as described in section 5.3.7.

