5.3.3 Summary Statistics

Data will be summarised by means of summary statistics. For continuous data the following summary statistics will be presented: number of observations, mean value, standard deviation, minimum, first quartile, median, third quartile and maximum value. Categorical data will be presented as counts and percentages. The data will be presented by visit. Baseline, demographics, primary endpoint, and key secondary endpoints will also be summarised by region.

Summary statistics will be presented by treatment group and assessment time and/or visit, as applicable.

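### The SAP drops the protocol's below/within/above-range laboratory shift table without declaring it, so no planned table counts subjects per arm who move above or below range

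*SAP*

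**What the plan says.** Protocol 12.1.13 fixes both the categories and the unit: "Shift tables will show the number of subjects who changed from below, within or above the reference range at baseline" and then "to below, within or above the reference range at end of treatment". It is a directional table, counted in subjects, with one post-baseline time point.

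SAP 5.3.12 uses other categories: "The number of normal, abnormal and clinically significant observations will be tabulated for each treatment group by visit, and in corresponding shift tables", running from baseline to every later visit. It counts observations and gives no direction.

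The same SAP paragraph also keeps continuous summaries. "For all laboratory parameters, summary statistics will be produced for observed values by visit"; and "In addition, the difference from baseline to each visit at which they were assessed will be derived and presented". SAP 5.3.3 defines the content of such summaries as "number of observations, mean value, standard deviation, minimum, first quartile, median, third quartile and maximum value". Abnormal values are flagged in listings.

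SAP 5.1 introduces its list of departures from the protocol with "Compared to these, the following changes have been implemented in the SAP" and names four: the Japan adjustment, extra subgroups, an added sensitivity analysis for lavage, and the number of lavages as an endpoint. The laboratory shift table is not among them.

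On the expected effect, Protocol 5.3 says that with significant systemic exposure "haematologic findings such as leucocytosis and neutrophilia may occur". Protocol 5.1 reports slight, dose-dependent white cell increases in phase I, mostly inside the reference range, and two related adverse events: eosinophilia and a raised white cell count.

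**The concern.** A shift table answers one safety question: how many subjects in each arm left the reference range, and on which side. For this drug the side is predicted, because molgramostim stimulates white cell production and any systemic effect should push counts up. Protocol 5.3 gives this as the reason for laboratory monitoring in the double-blind period. A table that merges low and high cannot answer the question. If the SAP is followed as written, the report will lack a display that the protocol promised, and the SAP's own list of changes will not say why.

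**Working it through.** No figure in the plan needs reproducing. The check sets the two tables side by side and then asks whether any other planned output supplies the missing count.

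**Step 1. Map the protocol's cells to the SAP's.** Assume that abnormal means outside the reference range, and set the clinical-significance split aside for the moment.

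| Protocol 12.1.13 movement | SAP 5.3.12 cell |
|---|---|
| within to within | normal to normal |
| within to below; within to above | normal to abnormal |
| below to within; above to within | abnormal to normal |
| below to below; below to above; above to below; above to above | abnormal to abnormal |

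Nine protocol cells (1 + 2 + 2 + 4 = 9) collapse into four. Splitting abnormal by clinical significance adds a grade but no sign. A subject moving from low to high at the same grade is shown as not having shifted. The by-visit category counts lose direction in the same way.

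**Step 2. Check the table shells.** In SAP Appendix 1, Tables 14.3.5.2 and 14.3.5.4 (double-blind) and 14.3.5.7 and 14.3.5.9 (follow-up) are titled as shift tables from baseline by visit. No title names categories, so the text of 5.3.12 governs.

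**Step 3. See whether other outputs give the count.**

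- *Continuous summaries (Table 14.3.5.1 for haematology).* Change from baseline is signed, so group direction is visible, but it is not related to the range. For observed values, a maximum above the upper limit shows that at least one subject exceeded it, and a third quartile above the limit shows that about a quarter or more did. With 45 per arm (SAP 3.2), 0.25 × 45 = 11.25. So any number from 1 (1/45 = 2.2%) to 11 (11/45 = 24.4%) can lie above the limit while the maximum is over it and the third quartile is not. This assumes complete data and one common upper limit.
- *Adverse event tables.* Preferred terms usually carry direction. Under Protocol 11.3, however, an asymptomatic laboratory finding becomes an adverse event only if it is judged clinically significant, is serious or leads to discontinuation.
- *Listings.* Individual values and reference ranges are listed (14.3.4.1, 14.3.4.2, 16.2.8.1, 16.2.8.2), so the count can be rebuilt, but only by hand.

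**Step 4. Scale.** In phase I, 2 of the 30 subjects given drug had a related white cell adverse event: 2/30 = 6.7%. Applied to 45 subjects this is 45 × 2/30 = 3, well inside the 1 to 11 band. The transfer is an assumption, since phase I was short dosing in healthy adults at several doses. Those two cases were also adverse events, which the SAP would tabulate by term. The figure shows only what size of count is at issue.

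**The case against.** A reader might infer that under the SAP a rise in white cells could not be told from a fall at all. The documents do not support that. The two sentences just before the shift-table sentence keep by-visit summaries of observed values and of signed change, clinically significant findings reach the adverse event tables under terms that state direction, and listings show each subject. This part of the objection stands and sets the limits of the point.

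The phase I rises were slight and mostly within range. Such rises would sit in the within-to-within cell of the protocol's own table too, and the change-from-baseline summary, which the SAP keeps, is the better display for them. That also stands. The directional table matters for subjects who actually leave the range.

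The SAP's categories are not invented. Protocol 10.4.6 has each value assessed as normal or abnormal, and then for clinical significance. They serve the safety endpoint on clinically significant laboratory changes, and the SAP's table covers every visit where the protocol's stops at end of treatment. That is a reason to keep the SAP's table, not to drop the other.

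Two further inferences should be resisted. One is that abnormal is a site judgement: Protocol 10.4.6 does not say who assigns it, and only clinical significance is expressly the investigator's assessment (Protocol 11.3). The other is that low values on placebo would mask high values on drug: the table's structure would allow it, but the documents give no frequency of low values in any arm.

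Finally, Protocol 12.3 lets deviations be described in an amendment, a revised SAP or the final report, so silence in SAP 5.1 is not by itself a breach. It does leave a reader of the SAP unaware that a promised table has gone.

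**Conclusion.** The point holds in a limited form. The protocol's directional laboratory shift table has been replaced, without declaration, by one that merges low and high, so no planned table gives the number of subjects per arm moving above or below range. The loss is of those counts, not of all directional information. It matters most for white cells, where leucocytosis, neutrophilia and eosinophilia are the anticipated findings and where up to 11 of 45 subjects could exceed the upper limit without the third quartile showing it.

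This concerns descriptive safety reporting only; no efficacy analysis or error rate is affected. The conclusion rests on the wording of the two sections and on reading abnormal as out of range. If abnormal were assigned on some other basis, the SAP's table would be further from the protocol's, and direction would still be missing.

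**What to change.** In SAP 5.3.12, add the below/within/above shift table of Protocol 12.1.13, counted in subjects and using the central laboratory's reference ranges. Name those categories in the shells for Tables 14.3.5.2 and 14.3.5.4. Do the same for Tables 14.3.5.7 and 14.3.5.9, since SAP 5.3.12 asks for similar safety summaries in both periods. Keep the SAP's by-visit normal / abnormal / clinically significant table alongside. If the sponsor means to drop the directional table, SAP 5.1 should list the change and give the reason.

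The cost is one or two sentences in the SAP, a few more descriptive tables and a small programming effort. Samples are analysed centrally (Protocol 10.4.6) and reference-range listings are already planned, so no new data are needed.
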